9.3. Variables

9.3.1. Variables and definitions

Table 3 summarises and defines the study variables to be collected and analysed in SNDS. Unless otherwise specified, these variables will be assessed during each patient's entire study period (baseline period and follow-up period).

This study will use code-based algorithms from the literature and/or other code lists to identify study variables. Published validated algorithms will be used where available.^{6, 7} All code-based algorithms and code lists will be reviewed and/or approved by Pfizer prior to

study initiation. Preliminary algorithms and/or codes are proposed in the following (Table 3); see also Annexes). Final algorithms and/or code lists may be refined as part of the statistical analysis plan (SAP) development. It is also to be noted that while laboratory tests performed are captured, results of laboratory tests are not available in the SNDS database.

Table 3. Operational definitions of study variables in Système National des Données de Santé

Variable	Role	Operational definition
Exposure		
Tofacitinib treatment	Exposure	Defined as having ≥1 ATC code (L04AA29) for a reimbursed prescription of tofacitinib during the indexing period. Index date is defined as the date of the first reimbursed prescription of tofacitinib.
Indication		
Indication	Indication (including off-label use)	Reported in the following categories: RA, PsA, UC and off-label/unknown based on hospital discharge diagnoses and active registration for diagnoses reported in the long-term disease (LTD) database for outpatients in the relevant time period. If there are no diagnosis codes for RA, PsA or UC, it will be categorised as off-label/unknown indications. Details will be further developed in the SAP.
		List of diagnoses codes for indications in ANNEX 13. LIST OF DIAGNOSIS CODES FOR INDICATIONS.
Primary Objective 1: I	Demographics, comorbi	dities and prior and current medications
		T OF CODES FOR COMORBIDITIES, unless otherwise
Age at tofacitinib initiation	Demographic	Calculated as the date of tofacitinib initiation minus the patient's month and year of birth and reported in the following categories: <18 years, 18-29 years and 30-39 years; 40-49 years; 50-59 years; 60-69 years; 70-79 years; ≥80 years; and <65 years and ≥65 years.
Sex	Demographic	Reported in the following categories: Male, Female and Unknown. Assessed on the date of the index tofacitinib prescription dispensing.

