Hepatic impairment	Comorbidity	Defined as ≥1 International Classification of Disease, 10th Revision (ICD-10) diagnosis code for hepatic impairment.
Hepatic impairment, mild or moderate	Comorbidity	Defined as ≥1 ICD-10 diagnosis code for mild or moderate hepatic impairment.
Hepatic impairment, severe	Comorbidity	Defined as ≥1 ICD-10 diagnosis code or procedure code for severe hepatic impairment.
Renal impairment	Comorbidity	Defined as ≥1 ICD-10 diagnosis code or procedure code for renal impairment
Renal impairment, mild	Comorbidity	Defined as ≥1 ICD-10 diagnosis code or procedure code for mild renal impairment
Renal impairment, moderate	Comorbidity	Defined as ≥1 ICD-10 diagnosis code or procedures code for moderate renal impairment
Renal impairment, severe	Comorbidity	Defined as ≥1 ICD-10 diagnosis code or procedure code for severe renal impairment
Herpes zoster (HZ)	Comorbidity	Defined as ≥1 ICD-10 diagnosis code for HZ.

Table 3. Operational definitions of study variables in Système National des Données de Santé

Variable	Role	Operational definition
Human immunodeficiency virus (HIV)	Comorbidity	Defined as ≥1 ICD-10 diagnosis code for HIV.
Tuberculosis (TB), including both active and latent TB	Comorbidity	Defined as ≥1 ICD-10 diagnosis code for TB.
Viral hepatitis B or C	Comorbidity	Defined as ≥1 ICD-10 diagnosis code for viral hepatitis B or C.
Serious and opportunistic infections of interest (including HIV, HZ, TB and viral hepatitis B and C)	Comorbidity	Defined as ≥1 ICD-10 diagnosis code for a serious and/or opportunistic infection of interest. Complete list in ANNEX 3. LIST OF DIAGNOSIS CODES FOR SELECT INFECTIONS OF INTEREST
Diverticulitis	Comorbidity	Defined as ≥1 ICD-10 diagnosis code for diverticulitis.
Malignancy (non- metastatic and metastatic, excluding NMSC)	Comorbidity	Defined as ≥1 ICD-10 diagnosis code for a malignancy (excluding NMSC).
NMSC	Comorbidity	Defined as ≥1 ICD-10 diagnosis code for NMSC.
Gastrointestinal perforation	Comorbidity	Defined as ≥1 ICD-10 diagnosis code for gastrointestinal perforation.
Interstitial lung disease	Comorbidity	Defined as ≥1 ICD-10 diagnosis code for interstitial lung disease. Complete list in ANNEX 6. LIST OF DIAGNOSIS AND PROCEDURE CODES FOR INTERSTITIAL LUNG DISEASE
Diabetes	Comorbidity	Defined as ≥1 ICD-10 diagnosis code for diabetes or ≥3 (or at least 2 in case of large pack sizes) prescription dispensing of oral antidiabetic agents and/or insulin (identified by ATC codes).

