9.4. Data sources

Data for this study will be obtained from SNDS database, which covers >99% (~ 65 million insures) of the French population from birth or immigration to death or emigration. The SNDS includes longitudinal claims data for inpatient and outpatient encounters by combining 3 main databases: the national hospital discharge database (PMSI), the health insurance claims database (Système National d'Informations Inter-Régimes de l'Assurance Maladie, SNIIRAM) and the national death registry. The PMSI was established in 2006 and captures information relating to inpatient or ambulatory care admissions to a public or private hospital in France. The SNIIRAM database captures data on socioeconomic characteristics and medical claims for medications, procedures and laboratory tests since 2003. The SNIIRAM database also includes the LTD registration data which captures information on the presence of LTD for which patients are eligible for 100% reimbursement of healthcare for the given disease. Data in the SNDS are updated bi-annually. Only variables relevant to this study, and available in the SNDS database, will be extracted.

As per the General Data Protection Regulation policy, only aggregated data with sample sizes >5 patients will be used for communications.

Details on the Health Insurance Data system, SNDS, are provided below in Table 4.

Table 4. Summary of Système National des Données de Santé database

Characteristics	SNDS
Database type	Claims
Country population	Over 65 million
Overall representativeness	Approximately 99% of the French population
Physician population	All
Expected number of tofacitinib	About 5,300 ^a
patients by the end of 2019	
Lag in data availability	12 months ^b

a Based on tofacitinib data from 2017-2019 that were obtained using the publicly available tools for querying the French national health registers

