ANNEX 11. LIST OF CODES FOR COMORBIDITIES

Comorbidity	Definition	Codes (ICD-10 codes, ATC codes, CCAM procedure codes)
Hepatic impairment	Defined as ≥1 ICD-10 diagnosis code for hepatic impairment.	K71 and K72
Renal impairment	Defined as ≥1 ICD-10 diagnosis code for renal impairment or a combination of EBM service	Stage III, IV or V (end stage) Chronic kidney disease
	codes, ICD-10 diagnosis codes and/or ICD-10 procedure codes.	ICD-10 diagnosis: Specific diagnoses of CKD Stage 3: N183 Stage 4: N184 Stage 5: N185 Other chronic renal disease: N188 and N189
		Diagnoses linked to CKD stage 5 Hypertensive cardionephropathy, with renal failure: I131 and I132 Extra-corporeal dialysis: Z491 Preparatory care for dialysis: Z490 Failure and rejection of a kidney transplant: T861 Dependence to kidney dialysis: Z992+1
		CCAM codes for medical procedures due to kidney failure (stage 5): JVJF002, JVJF004, JVJF003, JVJF005, JVJF006, JVJF007, JVJF008, JVRP004, JVRP007, JVRP008 and YYYY007 [TBC IN LAST VERSION]
Diabetes	Defined as ≥1 ICD-10 diagnosis code for diabetes or at least 3 reimbursements (or at least 2 in case of large pack sizes) of oral antidiabetes agents and/or insulin.	ICD-10 diagnosis: E10-E14 ATC code medications: A10*
Herpes zoster	Defined as ≥1 ICD-10 diagnosis code for herpes zoster.	B02*
Human immunodeficiency virus	Defined as ≥1 ICD-10 diagnosis code for human immunodeficiency virus.	B20-B24 and Z21
Tuberculosis, including both active and latent TB	Defined as ≥1 ICD-10 diagnosis code for tuberculosis.	
Viral hepatitis B or C	Defined as ≥1 ICD-10 diagnosis code for viral hepatitis B or C.	B180, B181 and B182

Comorbidity	Definition	Codes (ICD-10 codes, ATC codes, CCAM procedure codes)
Diverticulitis	Defined as ≥1 ICD-10 diagnosis code for diverticulitis.	Q396, Q696, K225, K382, N323, Q430, K314, N361 and C173
Malignancy (non-metastatic and metastatic, excluding non-melanoma skin cancer)	Defined as ≥1 ICD-10 diagnosis code for a malignancy (excluding non-melanoma skin cancer).	See table below
Non-melanoma skin cancer	Defined as ≥1 ICD-10 diagnosis code for non-melanoma skin cancer.	C44 other malignant tumour of the skin
Gastrointestinal perforation	Defined as ≥1 ICD-10 diagnosis code for gastrointestinal perforation.	K285

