Hypertension	Defined as ≥1 ICD-10 diagnosis code for hypertension or at least 3 reimbursements (or at least 2 in case of large pack sizes) of antihypertensive in the 12 months prior to or on the day of the index tofacitinib dispensing.	I10-I15
Prior myocardial infarction	Defined as ≥1 ICD-10 diagnosis code for a myocardial infarction in the 3 months prior to or on the day of the index tofacitinib dispensing.	I20-I25
Heart failure	Defined as ≥1 ICD-10 diagnosis code for heart failure in the 12 months prior to or on the day of the index tofacitinib dispensing.	I50, I110, I130 and I132
Inherited coagulation disorder	Defined as ≥1 ICD-10 diagnosis code for inherited coagulation disorder while receiving tofacitinib therapy.	D680, D681, D682, D66, D67, D689 and D686
Coronary heart disease	Defined as ≥1 ICD-10 diagnosis code for coronary heart disease.	I20-I25, I77 and Z95
Stable angina pectoris	Defined as ≥1 ICD-10 diagnosis code for stable angina pectoris.	I208 and I209
Hypercholesterolemia or dyslipidaemia or atherosclerosis	Defined as ≥1 ICD-10 diagnosis code for hypercholesterolemia or dyslipidaemia or atherosclerosis and ATC codes LLTs (statins, fibrates etc).	ICD-10: E780, E782, E783, E784, E785, E788, E789, Z863 and I70 ATC codes Statins: C10BA05, C10AA04 C10AA02, C10AA08, C10AA03, C10AA07 and C10AA01 ATC codes Fibrates: C10AB
Epstein-Barr virus (EBV)	Defined as ≥1 ICD-10 diagnosis code for Epstein-Barr virus.	D823, B348, B270, P358 and Z228
Hepatitis B virus (HBV)	Defined as ≥1 ICD-10 diagnosis code for Hepatitis B virus.	B181
Human papillomavirus (HPV)	Defined as ≥1 ICD-10 diagnosis code for HPV.	A630

Comorbidity	Definition	Codes (ICD-10 codes, ATC codes, CCAM procedure codes)
Human T-cell lymphotropic virus (HTLV)	Defined as ≥1 ICD-10 diagnosis code for human T-cell lymphotropic virus.	Z226, L303, B333 and B973
Hepatitis C virus (HCV)	Defined as ≥1 ICD-10 diagnosis code for hepatitis C virus.	B182 and B171
Coronary artery procedures*	Replacement of the ascending thoracic aorta and horizontal aorta with aortic valve replacement, with reimplantation of the coronary arteries, by thoracotomy with extracorporeal circulation	CCAM procedure code: DGKA014
	Ascending thoracic aorta replacement without aortic valve replacement, with coronary artery reimplantation, by thoracotomy with extracorporeal circulation	CCAM procedure code: DGKA003

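### Applied as written, two preliminary Annex 11 code lists (viral hepatitis B or C; gastrointestinal perforation) would under-capture descriptive Objective 1 comorbidities

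*Protocol*

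**What the plan says.** Table 3 (section 9.3.1) lists both variables as Primary Objective 1 comorbidities. Viral hepatitis is "Defined as ≥1 ICD-10 diagnosis code for viral hepatitis B or C", with no restriction to chronic disease. Gastrointestinal perforation has the same generic form, repeated in Annex 11 as "Defined as ≥1 ICD-10 diagnosis code for gastrointestinal perforation". Neither entry sets its own time window, so by the section's default both are assessed over the baseline and follow-up periods. Section 9.7.1 has them tabulated descriptively.

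Annex 11 supplies the codes:

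- Gastrointestinal perforation: K285 only.
- Viral hepatitis B or C: "B180, B181 and B182".
- HBV, defined as "Defined as ≥1 ICD-10 diagnosis code for Hepatitis B virus": B181 only.
- HCV: B182 and B171.

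On the status of the lists, section 9.3.1 says "Preliminary algorithms and/or codes are proposed in the following (Table 3); see also Annexes" and "Final algorithms and/or code lists may be refined as part of the statistical analysis plan (SAP) development".

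**The concern.** A code list should implement the definition beside it, and a combined variable should contain everything in its components. Neither holds here. The combined hepatitis row omits a code that the annex itself assigns to hepatitis C. The perforation row uses one four-character code for a variable defined without limit of site or cause, whereas other Annex 11 rows use whole categories (K71 and K72 for hepatic impairment, E10-E14 for diabetes).

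At stake is the accuracy of two lines in the Objective 1 comorbidity tables. If the perforation list is too narrow, a low count could be read as a low frequency of perforation when it reflects only the code chosen. The UC group makes this more relevant, because section 7 describes UC as a disease of the colon and rectum.

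**Working it through.** The protocol gives no figure to reproduce, so the check compares code sets.

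**Hepatitis (from Annex 11 alone)**

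| Code | Combined B or C row | HBV row | HCV row |
|---|---|---|---|
| B171 | no | no | yes |
| B180 | yes | no | no |
| B181 | yes | yes | no |
| B182 | yes | no | yes |

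- Combined row = {B180, B181, B182}.
- HBV row ∪ HCV row = {B181} ∪ {B182, B171} = {B171, B181, B182}.
- In the single-virus rows but not the combined row: {B171}.
- In the combined row but in neither single-virus row: {B180}.

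Four distinct codes appear across the three rows, and the combined row holds three of them. The two mismatches differ in effect. B171 matters for the Table 3 variable: a patient with only that code has hepatitis C by the annex's own HCV row but is not counted under B or C. B180 is already counted under B or C, so its absence from the HBV row costs the Table 3 variable nothing; it shows only that the rows were not built from one another.

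In standard ICD-10, B17.1 is acute hepatitis C, while the B18 codes are chronic. Its presence in the HCV row suggests that acute disease was meant to count. If so, acute hepatitis B (B16) belongs as well, and it appears in none of the three rows.

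**Gastrointestinal perforation**

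1. Definition: any ICD-10 code for gastrointestinal perforation (Table 3 and Annex 11).
2. Codes listed: {K285}, one code.
3. Meaning of K285: the protocol does not give it. In standard ICD-10, K28.5 is a chronic or unspecified gastrojejunal ulcer with perforation.
4. Ulcer perforation in the same classification: four categories (K25, K26, K27, K28), each with four perforation subcodes (.1, .2, .5, .6), so 4 × 4 = 16. The annex lists 1 of the 16.
5. Diverticular perforation (K57.0, K57.2, K57.4, K57.8) and perforation of intestine (K63.1): none listed.

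These are counts of codes, not of patients. The protocol says nothing about how often each code is used in SNDS, so they do not convert into a number of missed patients.

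**Reach of the two variables**

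Neither appears among the VTE, CV or malignancy risk factors or scores in Table 3, in the regressions of section 9.7.2.4 or 9.7.2.5, or in the study-size calculation of section 9.5. The contraindications in section 9.7.2.3.1 do not include perforation, and the serious or opportunistic infection outcome takes its codes from Annex 3.

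**The case against.** The strongest reply is that the lists are provisional. Section 9.3.1 states "All code-based algorithms and code lists will be reviewed and/or approved by Pfizer prior to" study initiation and leaves refinement to the SAP, which is not at hand. Section 9.9.1.2 adds that published, validated algorithms will be used where available. This stands to the extent that one cannot say the comorbidities are misreported: they would be under-captured only if the annex went forward unchanged. It does not remove the point, because a stated list that conflicts with another row of the same annex is an error in the document now. Annexes 3 to 9 each carry a line saying their codes will be reviewed or verified and updated; Annex 11 does not (nor do Annexes 10, 12 and 13). Within Annex 11 only the kidney and coronary procedure codes are marked as open.

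A second reply is that the perforation half relies on the meaning of a code that the protocol does not spell out. That is fair, and is why the list should be confirmed against the SNDS version of ICD-10. The mismatch between a generic definition and a single code is visible without it.

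Three stronger readings are tempting but unsupported:

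- That the reported hepatitis results would be irreconcilable. Only the combined variable is in Table 3; the HBV and HCV rows have no entry there, so conflicting counts would not arise among the specified variables.
- That the perforation row would be almost empty and then suppressed. Section 9.4 does say that "only aggregated data with sample sizes >5 patients will be used for communications", but the protocol gives neither the frequency of perforation nor the share coded K285. The rule also limits what is communicated; it does not make a result false.
- That acute hepatitis B is captured nowhere in the study. Table 3 has a separate infection variable that includes hepatitis B and C and uses Annex 3, whose code files are not shown.

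**Conclusion.** The point holds as a minor one. If Annex 11 is applied as written, the hepatitis B or C variable misses patients whose only code is B171, and the perforation variable misses every perforation not coded K285. The hepatitis omission is provable from the annex alone, although the annex does not itself settle which row is right. The perforation shortfall rests on one assumption, that K285 carries its standard ICD-10 meaning in SNDS.

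The size of either under-count cannot be derived from the protocol. The hepatitis gap is probably small, since on the standard meanings it concerns acute infection only. The consequence is limited to the descriptive Objective 1 tables.

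**What to change.** Before the extraction criteria are passed to the data holder:

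1. Define viral hepatitis B or C as the union of the HBV and HCV rows. Add B171 to the combined row and place B180 in the HBV row. State whether acute disease is intended; if it is, as B171 implies, add the acute hepatitis B codes (B16).
2. Expand the perforation row to match its Table 3 definition: the ulcer-perforation codes (K25-K28 with .1, .2, .5, .6), the diverticular-perforation codes (K57.0, K57.2, K57.4, K57.8) and perforation of intestine (K63.1). Confirm each against the ICD-10 version used in SNDS. If a narrower variable was meant, rename it and restate the definition.
3. Add to Annex 11 the review-and-update line that Annexes 3 to 9 carry.

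The cost is an edit to a few code rows, with no change to design, sample size or analysis and no new data source. It is cheapest before extraction, because section 9.4 limits the extract to variables relevant to the study.

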Prior MI	Outcome: changes	Defined as ≥1 ICD-10 diagnosis code for an MI in the 3
	in use in patients	months prior to the index tofacitinib dispensing.
	with VTE risk	
	factors	
History of heart failure	Outcome: changes	Defined as ≥1 ICD-10 diagnosis code for heart failure in the
, ,	in use in patients	12 months prior to the index tofacitinib dispensing.
	with VTE risk	
	factors	
History of combined	Outcome: changes	Defined as ≥1 reimbursed prescription of a combined
hormonal	in use in patients	hormonal contraceptives and/or hormonal replacement
contraceptives or	with VTE risk	therapy (as identified by ATC codes) in the 12 months prior
hormonal replacement	factors	to the index tofacitinib dispensing.
therapy		
History of inherited	Outcome: changes	Defined as ≥1 ICD-10 diagnosis code for inherited
coagulation disorder	in use in patients	coagulation disorder in the 12 months prior to the index
	with VTE risk	tofacitinib dispensing.
	factors	torustamo dispensing.
History of malignancy	Outcome: changes	Defined as ≥1 ICD-10 diagnosis code for malignancy
(non-metastatic and	in use in patients	(excluding NMSC) in the 12 months prior to the index
metastatic, excluding	with VTE risk	tofacitinib dispensing.
NMSC)	factors	
Age ≥65 years	Outcome: changes	Defined as age at tofacitinib initiation ≥65 years.
1150 -00 / 0410	in use in patients	2011100 as ago at totacidino initiation =00 yours.
	with VTE risk	
	factors	
	1401015	

Table 3. Operational definitions of study variables in Système National des Données de Santé

Variable	Role	Operational definition
History of diabetes	Outcome: changes in use in patients with VTE risk factors	Defined as ≥1 ICD-10 diagnosis code for diabetes or ≥3 (or at least 2 in case of large pack sizes) prescription dispensing of oral antidiabetic agents and/or insulin (identified by ATC codes) in the 12 months prior to the index tofacitinib dispensing.
History of hypertension	Outcome: changes in use in patients with VTE risk factors	Defined as ≥1 ICD-10 diagnosis code for hypertension or ≥3 (or at least 2 in case of large pack sizes) prescription dispensing of antihypertensive agents (identified by ATC codes) in the 12 months prior to the index tofacitinib dispensing. ANNEX 8. LIST OF ATC CODES FOR ANTIHYPERTENSIVES

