Initiating tofacitinib with ≥1 VTE risk factor(s)	Outcome: changes in use in patients with VTE risk factors	Defined as ≥1 VTE risk factor(s) (as listed and defined above) identified in the 12 months prior to the index tofacitinib dispensing.
Initiating tofacitinib with ≥1 VTE risk factors other than CV or malignancy risk factors	Outcome: changes in use in patients with VTE risk factors	The same definition as above but only limited to VTE risk factors other than CV or malignancy risk factors.
VTE risk factor scores	Outcome: changes in use in patients with VTE risk factors	Calculated as the sum of the number of VTE risk factors (as listed and defined above) identified in the 12 months prior to the index tofacitinib dispensing. Weighting of VTE risk factors may be considered as a sensitivity analysis to reflect the potential different
Number of UC patients with: ≥1 VTE risk factor; no prior alternative therapy (i.e., biologic); and an ADD >10 mg in Weeks 17-24, Weeks 25-32, Weeks 33-40 or Weeks 41-48 of follow-up	Outcome: changes in use in patients with VTE risk factors	importance of each risk factor. Defined as an UC patient meeting all of the following criteria: ≥1 VTE risk factor(s) (as listed and defined above) 12 months prior to the index tofacitinib prescription dispensing; 0 prescription medication dispensing for a biologic (as identified by ATC codes) in the 12 months prior to the index tofacitinib prescription dispensing; and an ADD of >10 mg in any of the intervals: Weeks 17-24, Weeks 25-32, Weeks 33-40 and Weeks 41-48 of follow-up (ADD defined in Section 9.3.3). Complete list of biologics in ANNEX 7. LIST OF ATC CODES FOR MEDICATIONS OF INTEREST TO AVOID WHILE TAKING TOFACITINIB.
Assessment of VTE risk; Section 9.3.2)	factors while receiving	tofacitinib therapy (duration of tofacitinib therapy defined in
VTE	Outcome: changes in use in patients with VTE risk factors	Defined as ≥1 ICD-10 diagnosis code for VTE while receiving tofacitinib therapy. List of VTE codes in ANNEX 12. LIST OF DIAGNOSIS CODES FOR VTE

Table 3. Operational definitions of study variables in Système National des Données de Santé

Variable	Role	Operational definition
Surgery, major	Outcome: changes in use in patients with VTE risk factors	Defined as ≥1 procedure code for a major surgery while receiving tofacitinib therapy.
MI	Outcome: changes in use in patients with VTE risk factors	Defined as ≥1 ICD-10 diagnosis code for an MI while receiving tofacitinib therapy.

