Variable	Role	Operational definition
Continuation of	Outcome: changes	Defined as patients aged <65 years when initiating
tofacitinib for patients	in use in patients	tofacitinib, who have ≥1 prescription dispensing of
who turn 65 years old	aged 65 years and	tofacitinib within a specific time window after turning 65
while receiving	older	years and ≥1 prescription dispensing for an alternative
tofacitinib with prior		therapy (i.e., biologic) prior to index tofacitinib prescription
use of alternative		dispensing.
therapies		
	endations for limitation	ons of use in patients with CV risk factors (will be stratified
		, and CV and malignancy report period 1, 2, 3)
Assessment of CV risk for	actors prior to initiation	n of tofacitinib
History of	Outcome: changes	Defined as ≥1 ICD-10 diagnosis code for hyperlipidaemia or
hyperlipidaemia	in use in patients	≥1 prescription dispensing (as identified by ATC code[s]) for
	with CV risk	a statin or other antihyperlipidaemic in the 12 months prior
	factors	to the index tofacitinib dispensing.
		Complete list in ANNEX 9. LIST OF ATC CODES FOR
		ANTIHYPERLIPIDAEMICS.
Age ≥65 years	Outcome: changes	Defined as age at tofacitinib initiation ≥65 years
	in use in patients	
	with CV risk	
	factors	
History of coronary	Outcome: changes	Defined as ≥1 ICD-10 diagnosis code for MI or stroke or ≥1
artery disease (defined	in use in patients	procedure code for CABG or PCI in the 12 months prior to
as MI, stroke,	with CV risk	the index tofacitinib dispensing.
coronary artery bypass	factors	
graft [CABG] or		
percutaneous coronary		
intervention [PCI])		
History of stable	Outcome: changes	Defined as ≥1 ICD-10 code for stable angina pectoris in the
angina pectoris	in use in patients	12 months prior to the index tofacitinib dispensing.
	with CV risk	
	factors	
Current or past	Outcome: changes	Defined as ≥1 ICD-10 diagnosis code for tobacco use
smoker ¹	in use in patients	disorder or ≥1 procedure code for counselling visits for
	with CV risk	smoking or ≥1 prescription dispensing (as identified by ATC
	factors	code[s]) for a nicotine replacement product in the 12 months
		prior to the index tofacitinib dispensing.
History of diabetes	Outcome: changes	Defined as ≥1 ICD-10 diagnosis code for diabetes or at least
	in use in patients	3 reimbursements (or at least 2 in case of large pack sizes) of
	with CV risk	oral antidiabetic agents and/or insulin in the 12 months prior
	factors	to the index tofacitinib dispensing.

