History of	Outcome: changes	Defined as ≥1 ICD-10 diagnosis code for hypertension or ≥1
hypertension	in use in patients	prescription dispensing (as identified by ATC code[s]) for an
	with CV risk	antihypertensive in the 12 months prior to the index
	factors	tofacitinib dispensing. Complete list in ANNEX 8. LIST OF
		ATC CODES FOR ANTIHYPERTENSIVES.

¹ Potential for very low sensitivity leading to misclassification. This variable will be reported if feasible

Table 3. Operational definitions of study variables in Système National des Données de Santé

Variable	Role	Operational definition
History of chronic kidney disease	Outcome: changes in use in patients with CV risk factors	Defined as ≥1 ICD-10 diagnosis code for chronic kidney disease in the 12 months prior to the index tofacitinib dispensing.
CV risk factor scores	Outcome: changes in use in patients with CV risk factors	Calculated as the sum of the number of CV risk factors (as listed and defined above) identified in the 12 months prior to the index tofacitinib dispensing. Weighting of CV risk factors may be considered as a sensitivity analysis to reflect the potential different importance of each risk factor.
Initiating tofacitinib with ≥1 CV risk factor (s)	Outcome: changes in use in patients with CV risk factors	Defined as ≥1 CV risk factor(s) (as listed and defined above) identified in the 12 months prior to the index tofacitinib dispensing (unless otherwise specified).
Initiating tofacitinib with ≥1 CV risk factor and no prior use of an alternative therapy (i.e., biologic)	Outcome: changes in use in patients with CV risk factors	Defined as ≥1 CV risk factor (as listed and defined above) identified in the 12 months prior to the day of the index tofacitinib dispensing and 0 prescription medication dispensing for an alternative therapy (i.e., biologic) in the 12 months prior to the date of the index tofacitinib prescription dispensing. Complete list of biologics in ANNEX 7. LIST OF ATC CODES FOR MEDICATIONS OF INTEREST TO AVOID WHILE TAKING TOFACITINIB.
Assessment of CV risk for versus < 65 years))	actors while receiving	tofacitinib therapy (will be stratified by sex and age (≥65 years

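### Annex 11 codes prior myocardial infarction as I20-I25, which contains the protocol's own stable-angina codes, so angina sets a VTE risk factor and can score twice for CV

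*Protocol*

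**What the plan says.** Three rows of Protocol Annex 11 matter.

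- **The row for MI before index:** "Defined as ≥1 ICD-10 diagnosis code for a myocardial infarction in the 3 months prior". The index day itself also counts, and the code cell reads I20-I25.
- **The row for coronary heart disease:** "I20-I25, I77 and Z95".
- **The row for stable angina:** I208 and I209.

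Protocol Section 9.3.1, Table 3, uses MI in three places.

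- **VTE factor before initiation:** "Defined as ≥1 ICD-10 diagnosis code for an MI in the 3", the figure being months before index.
- **VTE factor on treatment:** "Defined as ≥1 ICD-10 diagnosis code for an MI while receiving tofacitinib therapy".
- **Part of the CV factor coronary artery disease, over the prior 12 months:** "Defined as ≥1 ICD-10 diagnosis code for MI or stroke or ≥1". CABG and PCI procedures are the other route into this factor.

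Stable angina is a separate CV factor in Table 3, also over 12 months. It is not on the VTE list. The CV score is "Calculated as the sum of the number of CV risk factors (as listed and defined above) identified in the 12 months prior". Section 9.5 gives each factor one point. Table 3 has no rule for a code that meets two factors.

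**The concern.** The two columns of the MI row disagree. The definition asks for a myocardial infarction code, while the code cell gives the whole range that the annex uses for the broader coronary heart disease row. A programmer who follows the code cell will flag patients whose only cardiac code is one that the protocol itself calls stable angina.

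Two sets of results are exposed.

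- **VTE.** Section 9.7.2.4.1 tabulates individual VTE factors, with recent MI as one of its examples. It compares the proportion with at least one factor by logistic regression and the VTE score by linear regression. It also reports UC patients with a VTE factor, no prior biologic and an ADD above 10 mg in the later intervals. An angina code inside the 3-month window can enter all of these as an MI.
- **CV.** Section 9.7.2.4.3 tabulates individual CV factors and regresses the CV score on reporting period. If the MI row supplies the MI part of coronary artery disease, one angina code fills two items of the score.

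**Working it through.** The check is one of code membership and the scoring rule. The protocol states no figure for this point that could be reproduced.

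**Step 1. Membership.** MI list: I20-I25. Angina list: I208 and I209. Both angina codes fall under I20, so both are inside the MI list.

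**Step 2. Scoring a patient whose only cardiac code is I208 or I209.**

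| Item (Table 3) | As written | Angina codes removed from MI list |
|---|---|---|
| Prior MI, VTE factor (code within 3 months of index) | 1 | 0 |
| Coronary artery disease via MI, CV factor (12 months) | 1 | 0 |
| Stable angina, CV factor (12 months) | 1 | 1 |
| CV points from this code | 1 + 1 = 2 | 0 + 1 = 1 |
| At least one CV factor | yes | yes |

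The first row follows directly from the annex, because the MI row there is worded for that 3-month window. The second row is an inference: no other MI code list is given. Taking the codes from the coronary heart disease row instead leads to the same double point, since I20-I25 is in it too.

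**Step 3. Effect on outcomes.**

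- Mean CV score: rises by *p*, the share of patients with an angina code in the prior 12 months and no other qualifying coronary artery disease event.
- Mean VTE score: rises by the share with an angina code within 3 months of index and no infarction code in that window.
- At least one VTE factor: changes only for those among the latter who have no other VTE factor, such as age 65 or over, hypertension or diabetes.
- At least one CV factor: unchanged by this overlap, because stable angina already qualifies.

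**Step 4. Size.** The documents do not give *p*. Under assumed values:

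| Assumed *p* | Added to mean CV score | As a share of a 0.20 difference |
|---|---|---|
| 1% | 0.01 | 0.01/0.20 = 5% |
| 2% | 0.02 | 10% |
| 5% | 0.05 | 25% |
| 10% | 0.10 | 50% |

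For scale, Table 6 considers differences of 0.10 to 0.55. Its formula, 2(1.96 + 0.84)²σ²/ε² with unrounded normal quantiles, reproduces the five rows checked. For example, SD 0.6 and difference 0.20 give 142, and SD 0.6 and difference 0.10 give 566.

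**Step 5. Contrast between periods.** The shift in the CV-score contrast between reporting periods 3 and 1 is *p*₃ − *p*₁. It is 0 if the share is stable. If the share fell from 5% to 2%, it would be 0.02 − 0.05 = −0.03. The last column of Step 4 therefore describes inflation of the level and is not a bias in the comparison.

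**The case against.** The strongest reply is that the list is not final. Section 9.3.1 calls the codes preliminary, subject to review before study initiation and to refinement in the SAP, and it prefers published validated algorithms where they exist. That makes the correction easy, but it does not make the stated range right. Annex 11's own notes on provisional content concern procedure codes, and nothing marks the MI range as doubtful.

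The second reply is that the annex row covers only the 3 months before or on index, so its use for 12-month coronary artery disease and for on-treatment MI is assumed. That stands as a limit. The VTE consequence is stated in the text; the other two are inferred from the absence of any other list.

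Third, the primary comparison in Section 9.5 is the proportion with risk factors in period 3 against period 1. The CV proportion does not move with this overlap, and a constant inflation cancels between periods. This also stands.

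A reader might go further in four ways that the documents do not support.

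- **Every angina patient becomes an MI patient.** For the VTE factor this is true only of a code inside the 3-month window.
- **MI is overstated by some large multiple.** Any such ratio needs rates of angina and infarction codes, and the protocol gives neither.
- **On-treatment MI would be misread as a safety result.** Section 7 does name MI as an important identified risk. However, Table 3 uses on-treatment MI as a marker of change in use, and Section 9.7.2.4.1 specifies only continuation or discontinuation after such a factor.
- **Factors in a summed score must never share codes.** Annex 11 lists I110, I130 and I132 for heart failure, and these lie inside its hypertension range I10-I15. Some codes denote two conditions.

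**Conclusion.** The MI code range in Annex 11 is wrong as written and should be corrected. An angina code within 3 months of index sets a VTE factor that the protocol does not list. This can raise the recent-MI proportion, the proportion with at least one VTE factor, the VTE score and the UC outcome that uses VTE factors.

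Provided the same list serves the other uses of MI, which is the natural reading but is not stated, one angina code also gives 2 CV points instead of 1 and overstates the coronary artery disease proportion. On-treatment MI, and with it continuation or discontinuation after a new VTE factor, would be affected in the same way.

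The added mean CV score is 0.01-0.10 for assumed shares of 1-10%; the true share is not in the documents. It would be wrong to conclude that the planned period comparisons are biased: they shift only if the share of affected patients changes between periods. The established fault is mislabelled individual factors and inflated levels.

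**What to change.** Before analysis, make three changes.

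1. In Annex 11, restrict the prior MI row to codes that denote myocardial infarction, so that I208 and I209 no longer meet it.
2. State that this list applies wherever Table 3 uses MI: the prior and on-treatment VTE factors, and the MI part of coronary artery disease before and during treatment.
3. Check that coronary artery disease and stable angina cannot both score from the same angina code.

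Do not add a general ban on shared codes between factors, because that would disturb the codes that legitimately denote two conditions.

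The cost is one annex cell and a sentence or two in Table 3 or the SAP. Narrowing the range calls for no additional data, and Section 9.3.1 already provides for refining the code lists.
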